8. TREATMENT OF PATIENTS

8.1. Administration of Investigational Medicinal Product

During the Treatment Period, patients will be randomized to receive IMP of either BA 180 mg + EZE 10 mg FDC, BA 180 mg, EZE 10 mg, or placebo once daily. Each daily allotment of IMP is comprised of 2 tablets and 1 capsule provided in a blister package. Patients will be instructed to ingest IMP orally once daily with or without food at a similar time every day. On clinic visit days, patients will be instructed to delay ingestion of IMP until all study procedures have been completed.

If the patient forgets to take IMP on nonclinic visit days, it may be taken up to 12 hours later the same day. After that time, the patient should not take IMP that day and should resume ingestion of IMP the following day. Details describing the reasons for missed doses should be documented in the patient's medical records and electronic case report form (eCRF). Extra IMP is provided and can be used, if needed, prior to the next visit or to replace an allotment of IMP that cannot be used because it is lost or damaged.

Other details regarding IMP, including description, supply and control, accountability, handling, and disposal are provided in [Section 9](#).

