9. INVESTIGATIONAL MEDICINAL PRODUCT

9.1. Description of Investigational Medicinal Product

Table 2: Investigational Medicinal Products

Product Name:	Investigational Medicinal Product	
	Bempedoic acid	Placebo to Match Bempedoic Acid
Dosage Form:	Film-coated tablets	Film-coated tablets
Unit Dose:	180 mg	Not applicable
Container/Closure:	9 count blister card with child resistant closures	9 count blister card with child resistant closures
Route of Administration:	Oral, daily at approximately the same time, with or without food	Oral, daily at approximately the same time, with or without food
Physical Description:		
Product Name:	Investigational Medicinal Product	
	Ezetimibe	Placebo to Match Ezetimibe
Dosage Form:	Over-encapsulated tablets	Capsules
Unit Dose:	10 mg	Not applicable
Container/Closure:	9-count blister card with child-resistant closures	9-count blister card with child-resistant closures
Route of Administration:	Oral, daily at approximately the same time, with or without food	Oral, daily at approximately the same time, with or without food
Physical Description:		
Product Name:	Investigational Medicinal Product	
	Bempedoic acid + ezetimibe FDC	Placebo to Match Bempedoic acid + ezetimibe FDC
Dosage Form:	Tablets	Tablets
Unit Dose:	180 mg/10 mg	Not applicable
Container/Closure:	9-count blister card with child-resistant closures	9-count blister card with child-resistant closures
Route of Administration:	Oral, daily at approximately the same time, with or without food	Oral, daily at approximately the same time, with or without food
Physical Description:		

Please see Pharmacy Manual for detailed storage requirements and instructions and additional information.

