9.3. Packaging and Labeling

Double-blind IMP will be packaged in blister packs. Each blister pack will contain a 9-day supply and 4 blister packs will be provided in the drug kit.

The IMP labels will include protocol number, MED ID number, patient identification number, lot number, site number and investigator name in addition to standard language regarding warnings and regulations, administration and storage of the product.

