9.4. Investigational Medicinal Product Adherence

At each clinic visit during the Treatment Period, designated clinical site staff will assess patient IMP intake adherence by counting the number of tablets that are returned as unused and by querying the patient with regards to daily intake. If the patient has not taken multiple doses as instructed, the patient will be queried for a reason, findings will be documented, and the patient will be counseled on the importance of carefully following all dosing instructions. Factors contributing to poor adherence will be determined and, if possible, remedied. Patients demonstrating poor adherence during the Treatment Period will continue to be counseled on the importance of carefully following all dosing instructions, but will not be removed from the study.

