APPENDIX 1. SCHEDULE OF EVENTS

Visit	S1 ¹	T1	T2	T3	T4 ²
Week	-2	0	4	8	12/EOS
Procedure	Day -16 to -5	Day 1	Day 29 ± 5	Day 57 ± 5	Day 85 ± 5
Informed Consent	X				
Enrollment Criteria	X	X			
Demographics	X				
Medical History	X				
Concomitant\Prohibited Medications	X	X	X	X	X
Adverse Event Recording	X	X	X	X	X
Physical Exam		X			X
Weight ³	X	X ³	X	X	X
Height/BMI	X				
12-Lead ECG ⁴		X			X
Vital Signs ⁵	X	X	X	X	X
Serology ⁶	X				
Serum Pregnancy/FSH ⁷	X				
Urine Pregnancy		X			
TSH	X				
Clinical Safety Labs ⁸	X	X	X	X	X
Basic Fasting Lipids ⁹	X	X	X	X	X
Special Fasting Lipids and Other Biomarkers ¹⁰		X			X
HbA _{1C}	X				
Plasma Trough Study Drug			X	X	X
Randomization		X			
Double Blind Drug Dispensing		X	X	X	
Drug Return			X	X	X

BMI = body mass index; ECG = electrocardiogram; FSH = follicle-stimulating hormone, HbA_{1C} = hemoglobin A_{1C}; TSH = thyroid-stimulating hormone.

NOTE: For patients who withdraw from IMP treatment, they will continue to have visits according to the protocol schedule. Safety assessments should include clinical safety and basic lipid laboratories (except for apoB and hs-CRP), adverse events, PE, vital signs, and ECGs. For patients who withdraw from IMP treatment, but refuse to come to the clinic for assessments, assessments will take place by phone. The telephone contacts will occur according the protocol schedule with information regarding current health status and to collect information on AEs (e.g., recent procedures, hospitalizations, and if the patient has died, the cause of death).

¹ An optional visit approximately 10 days later MAY be completed if patient fails to meet specified entry criteria. If this optional visit is completed, the repeat value will be used to determine eligibility.

² All procedures will be completed at end of study or early termination.

³ Body weight will be measured in the morning while fasting, using consistent scales, after voiding, and without shoes and outerwear (e.g., coats).

⁴ Single 12-lead ECG will be collected prior to any blood sample collection.

⁵ Vital signs will include SBP, DBP, and HR, and will be collected prior to any blood sample collection. Patient will rest for 5 minutes prior to assessments.

⁶ Serology for Hep B antigen, Hep C antibody.

⁷ FSH completed in appropriate postmenopausal women only; pregnancy test completed in non-postmenopausal women only.

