5.2.9 Study Drug Exposure and Compliance

The length of exposure to study drug (FDC, BA, EZE or placebo) will be calculated as the number of days from the first dose of double-blind study drug to the last dose of double-blind study drug, regardless if the patient missed one or more doses of study drug. Length of exposure will be summarized by treatment group using descriptive statistics for the safety population.

The overall compliance to study drug calculated based on tablet count will be summarized by treatment group using summary statistics. The number and percentage of patients who were compliant with taking study drug will be summarized by treatment group for the safety population for the following categories <80%; >= 80%. Overall compliance will be calculated as: $100 * (\text{Total Dispensed Tablets} - \text{Total Returned Tablets}) / \text{Treatment Duration in day}$. Overall compliance during the study will be calculated by using study drug dispensation data.

The study drug administration and compliance data, including reasons for poor compliance, will be listed for each patient.

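### The compliance formula in SAP 5.2.9 has no tablets-per-day factor, so full intake at two tablets a day computes to 200% and the 80% cut-off falls at 40% of the tablets due

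*SAP*

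**What the plan says.** SAP section 5.2.9 sets out the compliance summary: "The overall compliance to study drug calculated based on tablet count will be summarized by treatment group using summary statistics". Patients in the safety population are then split at 80%. The formula reads: "Overall compliance will be calculated as: $100 * (\text{Total Dispensed Tablets} - \text{Total Returned Tablets}) / \text{Treatment Duration in day".

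The same section defines length of exposure as "the number of days from the first dose of double-blind study drug to the last dose of double-blind study drug", but does not say that this is the treatment duration used in the compliance formula.

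The protocol supplies the daily quantity in section 8.1: "Each daily allotment of IMP is comprised of 2 tablets and 1 capsule provided in a blister package". Section 9.4 has site staff assess adherence by "counting the number of tablets that are returned as unused", together with questioning the patient. On supply, section 9.3 says: "Each blister pack will contain a 9-day supply and 4 blister packs will be provided in the drug kit". The schedule in Appendix 1 marks "Double Blind Drug Dispensing" at visits T1, T2 and T3. Table 2 in section 9.1 gives the dosage form of the ezetimibe unit as "Over-encapsulated tablets".

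**The concern.** A count of tablets divided by a count of days is a proportion only if one tablet is due per day. Here two are due, plus a capsule, in every arm. Nothing in section 5.2.9 converts days to tablets due, and nothing there or in the protocol defines a tablet as one day's allotment.

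The prespecified split at 80% is what suffers. The cut-off is applied to a number that is twice the true percentage, so it separates patients at the wrong level of intake and hides poor adherence. The continuous summary is affected too, but every arm is scaled equally, so halving recovers it. Category counts cannot be recovered in that way; patients have to be reclassified.

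Two inputs are also left open. Treatment duration is not tied to the exposure definition in the same section. The handling of the capsule is not stated: because the ezetimibe unit is an over-encapsulated tablet, a count could cover two or three units a day. A count of tablets alone would, in the ezetimibe arm, cover only placebo.

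**Working it through.** The documents give no compliance result, so there is no figure to reproduce. The check is arithmetic on the formula.

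**Inputs**

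- Formula and 80% cut-off: SAP 5.2.9.
- Units due per day: 2 tablets and 1 capsule (protocol 8.1).
- Pack contents: 4 packs x 9 days per kit (protocol 9.3).
- Dispensing at T1, T2 and T3 (protocol Appendix 1). Assumption: one kit each time.
- Dosing days: 12 weeks x 7 = 84 (assumption for a patient who completes treatment).

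**General result.** Let k be the units due per day, D the treatment days and a the share of units due that were taken. The formula gives

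100 x (k x D x a) / D = 100 x k x a.

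Duration cancels. The 80% cut-off is met at a = 0.80 / k.

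**Illustration with k = 2, D = 84.** Dispensed: 3 x 4 x 9 = 108 daily allotments = 216 tablets. Due: 2 x 84 = 168. At full intake 48 are returned, and (216 - 48) / 84 = 200%.

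| Share of tablets due taken | Tablets taken | As written | Divided by 2 x days |
|---|---|---|---|
| 100% | 168 | 200% | 100% |
| 80% | 134.4 | 160% | 80% |
| 60% | 100.8 | 120% | 60% |
| 50% | 84 | 100% | 50% |
| 40% | 67.2 | 80% | 40% |
| 39% | 65.5 | 78% | 39% |

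The cut-off as written is 0.80 x 84 = 67.2 tablets, and 67.2 / 168 = 40%. With 85 days it is 68 / 170 = 40%. With the corrected denominator it is 134.4 of 168 tablets, or 80%.

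**Other readings of the count**

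- Capsule also counted (k = 3): full intake gives 300%, and the cut-off falls at 0.80 / 3 = 26.7% of units due.
- One daily allotment counted as one unit (k = 1): (108 - 24) / 84 = 100% at full intake, and the cut-off falls at 80%. Only this reading makes the formula work.

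**Effect of the duration definition.** If duration is last dose date minus first dose date without adding 1 (83 days), full intake is 168 / 83 = 202.4% as written and 168 / 166 = 101.2% with the factor of 2.

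**The case against.** The best case for the plan is that the unit is undefined rather than doubled. Table 2 describes each product's blister card as holding nine, and each pack is a nine-day supply, which fits one count per day. Section 5.2.9 says that compliance will be computed from dispensation data; if those data are held per blister position or per product, the formula returns 100% at full intake. Section 9.4 mentions only tablets, although the active unit in the ezetimibe arm is the capsule, so the word may be used loosely for any study drug unit. On that reading, dividing by 2 x days would turn full intake into 50% and push compliant patients below the cut-off.

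The packaging text does not carry that far. It describes how the drug is packed and does not define a tablet as an allotment. Section 8.1 distinguishes the two tablets from the capsule, and SAP 5.2.9 and protocol 9.4 both refer to a tablet count. What does stand is the warning about the remedy: the denominator must match the unit actually recorded, so that unit has to be confirmed before a factor is applied.

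It is also fair to say that little depends on this summary. The imputation rule uses days since last dose, the treatment completer set uses the end of treatment form plus a Week 12 LDL-C value, and the sensitivity and subgroup analyses do not use compliance. No compliance table is listed in either SAP addendum. Values near 200% would probably be noticed. That limits the consequence; it does not make the written rule correct.

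**Conclusion.** The formula is wrong as written. At two tablets a day it returns twice the true percentage, and the 80% cut-off falls at 40% of the tablets due, so patients who took from 40% to just under 80% over their treatment duration are classed as compliant. This follows from SAP 5.2.9 and protocol 8.1 alone. The 84 days and the three kits only illustrate it. It assumes that the count is of tablets, as both documents say; if the capsule is counted too, the cut-off falls to 26.7%.

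The error affects one descriptive summary and its two-category table, with no effect on the efficacy conclusions. It should be corrected because that table is a prespecified output and the correction is small. The documents contain no intake data, so the number of patients who would change category is unknown.

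**What to change.** - State which unit is counted. If it is tablets, divide by 2 x treatment days. If it is a complete daily allotment, say so and keep days as the denominator. Keep the 80% cut-off.
- Define treatment duration, for example last dose date minus first dose date plus 1.
- State whether and how the capsule is counted. A tablets-only count leaves active drug unmeasured in the ezetimibe arm.
- Both SAP addenda say that the planned analyses were completed. The sponsor should therefore confirm which denominator was programmed and, if it was the written one, reissue the table.

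The cost is one corrected line and two definitions. Reported tablet compliance halves, and any patient between 40% and 80% moves to the lower category.

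Two limits remain after the change. If duration ends at the last dose, a patient who takes every tablet for 34 of 84 days and then stops scores 68 / 34 = 200% as written and 68 / 68 = 100% after correction, so early stopping stays invisible. Lost or damaged allotments that are not returned still count as taken.

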9.5. Investigational Medicinal Product Accountability

Patients will be instructed to return all packaging and unused IMP at every visit for assessment of adherence and drug accountability.

Accurate records of the receipt of all IMP shipped by the Sponsor (or designee) and the disposition of that IMP must be maintained.

IMP records or logs must comply with applicable regulations, local law, and guidelines, and should include:

- Amount received/placed in storage area;
- Amount currently in storage area;
- MED ID number for all IMP;
- Dates and initials of person(s) responsible for IMP inventory (including entry/movement/disposition);
- Date and amount of IMP dispensed to each patient, including unique patient identifiers;
- Date that IMP was returned by patient, assessment of adherence, and relevant documentation of discrepancies;

- Nonstudy disposition (e.g., lost, broken, wasted);
- Amount returned to Sponsor (or designee)/destroyed or amount destroyed per local standard operating procedure (SOP) following accountability by site monitor.

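### The SAP compliance formula has no term for lost, damaged or unreturned drug, so a patient with such stock can be scored above true intake and across the 80% cut

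*SAP*

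**What the plan says.** SAP 5.2.9 defines overall compliance as 100 × (total dispensed tablets − total returned tablets) ÷ treatment duration in days, and adds that "Overall compliance during the study will be calculated by using study drug dispensation data". The result is summarized by arm for the safety population, and patients are split into below 80% and 80% or more. The section does not define treatment duration. It does define length of exposure, which runs "from the first dose of double-blind study drug to the last dose of double-blind study drug, regardless if the patient missed" doses in between.

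The protocol supplies the context:

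- Section 8.1: "Each daily allotment of IMP is comprised of 2 tablets and 1 capsule provided in a blister package". Extra drug is provided, among other uses, "to replace an allotment of IMP that cannot be used because it is lost or damaged".
- Section 9.3: "Each blister pack will contain a 9-day supply and 4 blister packs will be provided in the drug kit".
- Section 9.4: sites assess adherence by counting returned tablets and by asking the patient about daily intake.
- Section 9.5: patients are told to bring back all packaging and unused drug at every visit. The sites' drug records include an item for "Nonstudy disposition (e.g., lost, broken, wasted".

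**The concern.** Subtracting returns from dispensed stock measures intake only if every unit not swallowed comes back. The protocol foresees that some will not: it supplies spares for lost or damaged allotments and has sites record losses. Its part on discontinuations also allows for patients who stop drug and no longer attend in person, who leave with an early visit only where possible, or who are lost to follow-up. Those patients are plausibly the least likely to hand back a kit. The SAP formula uses neither the loss records nor the intake query.

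At stake is the one by-arm compliance percentage that the SAP plans, with its 80% split. Readers will use it when judging whether the arms took their drug to a similar extent. A correction of the tablets-per-day unit alone would leave a plausible-looking percentage that can still be too high.

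**Working it through.** The documents state no compliance result, so there is no figure to reproduce. The check applies the formula to worked patients.

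**Inputs**

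- Kit size: 4 blisters × 9 days = 36 daily allotments (Protocol 9.3).
- Dispensing at T1, T2 and T3 (Protocol 10.5.2 to 10.5.4). Assumption: one kit per visit, so 3 × 36 = 108 allotments. Appendix 7 supports this by giving the 4-week interval as the reason for four blisters.
- Duration for a completer: 84 days. Cut-off: 80% (SAP 5.2.9).
- Unit: the daily allotment. Read literally, the formula divides tablets by days although two tablets are due each day, which doubles every score. That is a separate defect and is taken as corrected here.

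**General form.** Let T be doses taken, U doses neither taken nor returned, and D days. Then returned = 108 − T − U, and

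score = (108 − returned) ÷ D = (T + U) ÷ D, against a true value of T ÷ D.

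The excess is U ÷ D. With D = 84, a patient reaches the upper category once T + U is at least 0.80 × 84 = 67.2.

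**All unused stock returned (U = 0).** The score equals T ÷ D. Patients at 40%, 50% and 70% score 40%, 50% and 70%.

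**One blister lost.** T = 61, U = 9. Returned = 108 − 61 − 9 = 38. Score = 70 ÷ 84 = 83.3%; true value = 61 ÷ 84 = 72.6%.

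**Third kit not returned.** T = 50, spread evenly, or 16.67 per kit. Returned from the first two kits = 2 × (36 − 16.67) = 38.67. Score = (108 − 38.67) ÷ 84 = 82.5%; true value = 50 ÷ 84 = 59.5%.

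**Nothing returned.** Score = 108 ÷ 84 = 128.6%, whatever the true intake.

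**Early stop, first kit not returned, last dose on Day 14.** The result depends on the undefined denominator:

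- First to last dose: 36 ÷ 14 = 257%, whether the patient took all 14 doses (true value 100%) or half of them (50%).
- Planned 84 days: 36 ÷ 84 = 42.9%, against at most 14 ÷ 84 = 16.7%. The patient stays below 80%.

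**Under the proposed rule.** The lost-blister patient scores (108 − 38 − 9) ÷ 84 = 72.6%. For the patient with the unreturned third kit, two evaluable intervals remain: (72 − 38.67) ÷ 56 = 59.5%. The Day-14 patient has no evaluable interval and is shown as such.

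**The case against.** The strongest reply is that the effect is conditional and its frequency unknown. Patients are told to return everything at every visit, and those who stop drug stay in follow-up, which gives later chances to return a kit. A single lost allotment adds only 1 ÷ 84 = 1.2 points; it takes a whole blister or kit to move the patients above. This stands: a reader might infer that poor adherers and early drop-outs are scored as compliant in general, and the documents do not support that.

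It is also fair that the SAP does not contradict the protocol. Protocol 9.4 relies on the same count of returned units. The SAP leaves the loss records unused, which is an omission.

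The early-stop figure needs care too. SAP 5.2.9 does not say that treatment duration means first to last dose. On that reading, a patient who took every dose to Day 14 belongs in the upper category and only the printed 257% is absurd. It would be visible, because SAP 5.1 requires the maximum to be reported.

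Finally, the table is not the only evidence on adherence. The SAP also plans length of exposure and a by-patient listing with reasons for poor compliance (5.2.9), reasons for withdrawal (5.2.4) and trough concentrations (5.3.5).

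None of this removes the defect. A stated formula gives a wrong figure in situations that the protocol anticipates, and the two completer examples do not depend on the choice between first-to-last dose and planned duration.

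**Conclusion.** The formula scores every unreturned unit as taken, so a patient with lost, damaged or unreturned stock can be placed above true intake and across the 80% cut: 72.6% becomes 83.3%, and 59.5% becomes 82.5%. These figures rest on one kit per visit, 84 days, the daily allotment as unit and, in the second case, even intake across kits. The 257% for a Day-14 stop holds only if duration runs from first to last dose.

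The number of patients affected, the shift in any arm mean and the arm most affected cannot be derived from the documents. A reader might infer that the error hides poor adherence most in the arm with most drop-out; without return rates and a defined denominator, that is not established.

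The consequence is confined to a descriptive summary. The completer set comes from the end-of-treatment form (SAP 5.2.1.3), and the imputation rule uses time since last dose (SAP 5.3.1). The compliance percentage enters neither, nor the co-primary model. This is a minor point worth correcting.

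**What to change.** In SAP 5.2.9:

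1. Define treatment duration for this calculation.
2. Subtract from the numerator the doses documented as lost, damaged or wasted under Protocol 9.5.
3. Leave any dispensing interval with an unreturned kit out of both numerator and denominator.
4. Show patients with no evaluable interval in a separate not-evaluable row, so that they are not counted at 80% or more.

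Settle the tablets-per-day unit in the same edit; these rules do not replace that correction.

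The cost is SAP wording and programming, provided that the loss records reach the analysis database. Protocol 9.5 requires the records at the site but does not say that they are transferred, so the sponsor must confirm this. If they are not, the rules for unreturned kits and the separate row can still be applied from dispensing and return data. The downside is that a few patients become not evaluable and the figures look slightly less favourable.
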